#### 5.3.1 Healthcare utilization and cost

Direct medical costs include cost of all medical care for the woman and newborn during the delivery hospitalization. These costs will be estimated using health care charges associated with each of these services. Unit costs will be adjusted by health system specific cost-to-charge ratios. If cost-to-charge ratios are not available, published ratios or in rare cases Medicaid reimbursements will be used.

The effect or outcome measure for cost effectiveness will be quality-adjusted life years (QALYs). Maternal and neonatal QALYs will be estimated by applying published utility weights (1=perfect health, 0=death) from various health states to components of the conditions found by sequencing. Cost-effectiveness of prenatal sequencing will be evaluated as the incremental cost per QALY with a threshold of less than \$100,000 per QALY as cost effective. Cost benefit analysis will also be performed and be evaluated by dividing the costs of care and outcomes from the intervention by the costs of usual care. A CBA < 1 indicates that the intervention is cost saving and thereby cost beneficial.

All estimates of costs and outcomes will be reported as means with 95% confidence intervals. Sensitivity analysis will be conducted to evaluate the impact of uncertainty on the results. Varying probabilities (e.g.

baseline risk of sequencing findings, change in neonatal outcomes) and cost parameters (e.g. cost of sequencing, healthcare costs) will be used to take into account potential clinical scenarios that might deviate from the baseline estimates. One-way deterministic sensitivity analysis for individual factors will be employed and Monte Carlo simulation to assess the robustness of the findings by simultaneously sampling distributions around multiple parameters within the model and report 95% confidence ellipses and acceptability curves.

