The study will determine, in a sequential population of pregnancies with selected fetal structural anomalies and a negative or non-causal chromosomal microarray (CMA), the frequency of pathogenic, likely pathogenic, and uncertain genomic variants identifiable by sequencing. To determine the impact of this information on clinical care, a control population of unsequenced pregnancies with similar structural anomalies will be prospectively recruited and the infants from both cohorts will be followed up to 1 year of age. Due to limited prospective enrollment of the controls, a portion of the unsequenced pregnancies will be enrolled retrospectively through medical record review. This study component will evaluate differences in healthcare management and cost through discharge from hospital post-delivery, and perinatal and infant outcomes through 1 year of life. The educational, counseling and psychosocial impact of sequencing results during the prenatal period, in the nursery and through 1 year of life also will be evaluated. The retrospective unsequenced pregnancies will not be included in 1-year follow-up, as they will be enrolled under a waiver of consent. Since the analytical and clinical tools needed for the full translation of sequencing into care are still developing, optimization of bioinformatic tools to improve identification of pathogenic and likely pathogenic mutations associated with prenatal phenotypes of established disease genes will be investigated, as well as identification of new genes associated with presently undiagnosed fetal/neonatal phenotypes. This study will provide an in-depth evaluation of the prenatal diagnostic value of sequencing prior to its responsible introduction into practice and will provide independent data to guide its translation.

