#### 2.2.3 Healthcare Utilization and Cost

Integration of WES or WGS into clinical care requires not only demonstration of the ability to identify the underlying etiology of a disorder but also requires evidence that care is improved, providing value to the health care system. While WGS is currently a relatively expensive test (≥\$15,000 per trio), the information may lead to significant alterations in care utilization. Given that healthcare costs can be \$250,000 or more in the first year of life for some complex congenital anomalies, the genetic diagnostic information may be net cost saving. Even if not cost-saving, if clinical outcomes are improved significantly, the incremental cost of WGS may be justifiable based on its cost effectiveness. Recent studies in critically ill neonates and infants have suggested that establishing a diagnosis leads to more focused management and reduction in healthcare utilization and reduced cost. Meng et al evaluated diagnostic WES for 278 critically ill infants within the first 100 days of life and found a genetic diagnosis in 36.7%. These new diagnoses led to care modification in 52%, including initiation of new subspecialist care, redirection of care, changes in medication/diet, or completion of major procedures (e.g., transplant). The greatest impact was in infants receiving rapid "critical trio sequencing". A metaanalysis found that change in clinical management by WGS results was 27% (4 studies with 136 children) compared with 17% by WES (12 studies and 992 children) and 6% by CMA (8 studies of 4,271 children). 40 Another study evaluating the cost-effectiveness of WES in a pediatric setting reported the mean duration of the diagnostic odyssey was 6 years, and that the diagnostic trajectory for WES performed at the initial tertiary presentation resulted in an incremental saving of \$6800 per additional diagnosis compared with the standard diagnostic pathway. In summary, studies have suggested that sequencing early in the disease course may provide the maximal benefit by modifying clinical management, reducing the time to diagnosis and cost.

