# 4.8 Healthcare Utilization and Change in Management

Information on healthcare utilization and charges will be collected starting at the time of presentation to the hospital for delivery through discharge. Site coordinators will work with hospital billing to obtain detailed billing records from delivery admittance through discharge for each study participant, including the hospital charge ratio. Current Procedural Terminology (CPT) medical code, description, total units and total hospital charge will be collected. At the 12-month follow-up phone call for participants who were enrolled prospectively, information will also be recorded on healthcare utilization post neonatal discharge, including number of infant hospitalizations, surgeries, procedures and specialist visits. For twin gestations, this information will only be collected for the twin with the anomaly.

To identify if sequencing results changed the original care plan, the site coordinators will review all prenatal and postnatal medical records in conjunction with the designated physician from diagnosis until discharge or death to document change in healthcare management. Change in healthcare management will be completed by both the MFM/OB for prenatal assessment and a designated neonatal fellow in consultation with the clinical care team at each institution. The survey will include questions focused on clinical utility, such as: 1) have there been any changes to the patient's treatment plan based on the sequencing results, 2) have there been any changes to the way that you counsel the patient/family regarding the immediate medical management as a result of the sequencing results, and 3) have there been any changes to the way that you counsel the patient/family regarding the long term medical management as a result of the sequencing results. The changes in healthcare management will be presented and reviewed by the Clinical Adjudication Committee which will confirm whether an alteration in health care management occurred based on sequencing results.

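### The cost-per-QALY ratio counts costs only to delivery discharge but gives its QALYs no time horizon, so the $100,000 label can be wrong in either direction

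*Combined protocol and SAP*

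**What the plan says.** All references are to version 1.8 unless stated.

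- **Costs.** Section 5.3.1: "Direct medical costs include cost of all medical care for the woman and newborn during the delivery hospitalization". Section 4.8 sets the same window for data collection: "Information on healthcare utilization and charges will be collected starting at the time of presentation to the hospital for delivery through discharge". Section 1.1 describes an aim to "evaluate differences in healthcare management and cost through discharge from hospital post-delivery, and perinatal and infant outcomes through 1 year of life", so it gives cost a shorter window than infant outcomes.
- **Effects.** Section 5.3.1: "Maternal and neonatal QALYs will be estimated by applying published utility weights" "from various health states to components of the conditions found by sequencing". No time horizon or discount rate is stated here or elsewhere.
- **Decision rule.** Section 5.3.1: "Cost-effectiveness of prenatal sequencing will be evaluated as the incremental cost per QALY with a threshold of less than" $100,000. The ratio is secondary outcome 9 in Section 4.10.2. It carries no asterisk, so it is not confined to participants enrolled prospectively.
- **After discharge.** At the 12-month contact with prospective participants, "information will also be recorded on healthcare utilization post neonatal discharge, including number of infant hospitalizations, surgeries, procedures and specialist visits" (Section 4.8). Table 2 shows this is by maternal self-report. These are counts without charges, and Section 5.3.1 does not cost them. Retrospective controls are followed only to delivery discharge (Section 4.6).
- **Scale.** Section 2.2.3 says costs can reach $250,000 or more "in the first year of life for some complex congenital anomalies", and puts sequencing at $15,000 or more per trio.

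**The concern.** A cost-effectiveness ratio can be read against a willingness-to-pay threshold only if costs and effects cover the same period. Here the cost period is explicit and short. The utility weights attach to genetic conditions, many of which last well beyond the birth admission, and nothing ties them to that admission.

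Suppose prenatal results lead to an extra surviving infant. That infant adds QALYs to the denominator, while readmissions, operations and specialist care after discharge add nothing to the numerator. If results instead reduce later care, or lead to fewer survivors, the later costs avoided are also missing. The ratio would be reported with a cost-effective or not-cost-effective label that the analysis cannot support.

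This matters because Section 2.3 presents the study as the first cost-effectiveness analysis of its kind. Section 2.2.3 also argues that sequencing may be justified on cost effectiveness even if it saves no money.

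**Working it through.** **The plan's own figures.** The documents give no cost-per-QALY estimate to reproduce. The one reproducible figure for cost is the power statement in Section 5.1: lognormal charges, mean $277,902, SD $389,484, 500 versus 300, ratio 0.80, stated power 80%. The log-scale SD is √ln(1 + (389,484/277,902)²) = 1.042. A two-sided 5% z-test on logs then gives 83.4% power, and the Mann-Whitney equivalent (SD divided by √(3/π)) gives 81.7%. The stated power is sound or slightly conservative, and this point does not depend on it.

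**Formula.** Per pregnancy, let dC be the incremental cost in the plan's window plus sequencing, s the extra survivors, Q the QALYs per extra survivor and L the post-discharge cost per extra survivor.

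- Ratio as planned: dC / (sQ)
- Ratio with later care counted: (dC + sL) / (sQ) = planned ratio + L/Q

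The omission L/Q does not depend on s or dC, so it remains whether or not the price of sequencing is included.

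**Inputs.** L and Q are assumptions. For Q, with an assumed 3% discount rate, T years at utility u give u × (1 − 1.03^−T)/0.03. This is 0.5 × 4.58 = 2.29 for 5 years at 0.5, 0.7 × 14.88 = 10.4 for 20 years at 0.7, and 29.7 for 75 years in perfect health. I therefore use Q = 2.5, 10 and 30. For L, $250,000 is the first-year figure in Section 2.2.3. That year includes the birth stay, which the plan already costs, so as a year-1 post-discharge cost it is an upper-side illustration. Smaller and larger values are shown because costs beyond year 1 are unknown.

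| L | Q = 30 | Q = 10 | Q = 2.5 |
|---|---|---|---|
| $50,000 | $1,667 | $5,000 | $20,000 |
| $100,000 | $3,333 | $10,000 | $40,000 |
| $250,000 | $8,333 | $25,000 | $100,000 |
| $500,000 | $16,667 | $50,000 | $200,000 |

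Each cell is L/Q, the dollars per QALY left out of the ratio.

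**Example with sequencing counted.** Take dC = $15,000, s = 0.02 (assumed) and Q = 10.

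- Planned ratio: 15,000 / (0.02 × 10) = $75,000, below the threshold.
- With L = $250,000: (15,000 + 5,000) / 0.2 = $100,000, no longer below it.
- With L = $500,000: (15,000 + 10,000) / 0.2 = $125,000.

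**Same check by year.** If later care costs a per year at utility u, and both are discounted alike over the same period, the omission is a/u whatever the horizon. $10,000 a year at u = 0.9 gives $11,111 per QALY; $50,000 a year at u = 0.5 gives $100,000.

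**If QALYs were cut to the cost window instead.** Over an assumed 30-day stay a survivor could gain at most 30/365.25 = 0.08 QALY. The windows would then match, but the ratio would ignore nearly all the benefit of survival, so the threshold would still be uninformative.

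**The case against.** The strongest reply is that this is an omission and not a stated contradiction: no section sets a lifetime or multi-year QALY horizon. That is correct, and a reader should not infer that one was chosen. The gap still matters, because the cost rule is definite. Followed exactly, it leaves later care uncosted under any horizon that lets the conditions last.

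A second reply is that Section 5.3.1 already varies healthcare costs and neonatal outcomes, one at a time and by Monte Carlo simulation, with acceptability curves. The curves do relieve dependence on a single threshold. But post-discharge cost is not a named parameter, and varying delivery-stay costs does not add a missing category.

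Three stronger readings are tempting, and the documents do not support them.

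- QALYs per survivor vary more than 300-fold between a 30-day and a 75-year horizon (29.7/0.08). That shows sensitivity to the horizon and does not measure the omitted-cost error, which is L/Q.
- The $250,000 cannot be treated as wholly uncounted, because it includes the birth stay.
- The bias cannot be said to favour sequencing. It reverses if sequencing lowers later costs, or if there are fewer survivors and the later costs avoided go uncounted.

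Finally, the ratio is one secondary outcome. The co-primary comparison of hospital charges is unaffected.

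**Conclusion.** The concern holds as a mismatch between a fixed cost window and an unspecified QALY horizon. The omitted amount is L/Q. At an assumed L of $250,000 it runs from about $8,300 per QALY at Q = 30, some 8% of the threshold, to $100,000 at Q = 2.5, the whole threshold. With extra survivors and positive later costs, the label changes when the planned ratio lies between $100,000 − L/Q and $100,000. If sequencing lowers later costs, the range at risk lies above the threshold instead.

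The documents support saying that the label can be wrong. They do not show that it will be, nor that the result depends mainly on this gap: with modest later costs and many QALYs per survivor, only ratios close to the threshold are affected. The size rests on assumed L, Q, s and discount rate. That post-discharge care is missing from the costs rests on the text alone.

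**What to change.** In Section 5.3.1:

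1. State one time horizon and one discount rate, and apply both to costs and QALYs.
2. Add post-discharge cost, with a range, as a named parameter in the one-way and Monte Carlo analyses already planned.
3. Use the 12-month utilization counts only as a rough check on year 1. They are self-reported, uncosted and limited to prospective participants. The amendment history says prospective control enrollment was not feasible, so the control side may be thin.
4. If post-discharge costs cannot be sourced, report the delivery-stay ratio as a short-term result and drop the $100,000 claim.

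The cost is revised wording and some extra modelling, with no new patient data. The drawback is that later costs would be assumed and not observed, so their ranges should be reported beside the result.

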# 3 Study Design

# 3.1 Design Summary

This multicenter, observational cohort study will evaluate prenatal sequencing among pregnancies with fetal structural anomalies recruited at university based medical centers and evaluated at four genetic laboratories. A total of 1,100 pregnancies with fetal structural anomalies and meeting eligibility criteria will be enrolled into the study. Of these, 750 will undergo prenatal genomic sequencing (prenatal sequencing group) and the remaining 350 pregnancies will not have any prenatal genomic sequencing (unsequenced prenatal group). Enrollment of pregnancies with an isolated nuchal translucency measurements  $\geq$  3.5 mm and < 4.5 mm without evidence of cystic hygroma will be restricted to 5% within each group (sequenced and unsequenced) and isolated estimated fetal weight <5th %ile also will be restricted to 5% for each group (sequenced and unsequenced).

The prenatal sequencing group will be used to determine the frequency of pathogenic, likely pathogenic, and uncertain genomic variants identifiable by sequencing and the relative yield of sequencing. The prenatal sequencing group will be compared with the unsequenced prenatal group (prospective and retrospective) to evaluate health care management, health care utilization and cost, and perinatal outcomes. The prenatal sequencing group will be compared with the prospective unsequenced prenatal group to evaluate psychosocial needs of pregnant couples. Mothers, fathers and infants will be followed through 1 year postpartum for participants enrolled prospectively.

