# 4.6 Study Procedures

Women who are enrolled prospectively will be followed from screening through 12 months postpartum unless a pathogenic or likely pathogenic causal CMA is reported prenatally or postnatally prior to neonatal discharge. Women who are enrolled retrospectively will be followed from screening through delivery discharge. For twin gestations, neonatal data will only be collected for the fetus with the anomaly. Data will be collected at the following time points:

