#### 4.10.2 Secondary Outcomes (Prenatal sequencing and unsequenced prenatal)

- 1. Perinatal outcomes including gestational age at delivery, major morbidities including mechanical ventilation, sepsis, pressor support, ECMO, metabolic abnormalities (e.g., acidosis, elevated uric acid, hypo-/hyperglycemia), intraventricular hemorrhage, periventricular leukomalacia, encephalopathy, and seizure
- 2. Neonatal/infant death at time of discharge and at 12 months of age\*
- 3. Length of initial NICU stay and number of days spent in the hospital between initial discharge and 12 months of age\*
- 4. Infant weight and length at 12 months of age\*

- 5. Developmental parameters (communication, gross motor, fine motor, problem solving and personal-social) at 12 months of age using ASQ-3\*
- 6. Anxiety following result disclosure (or 4 weeks post enrollment for the unsequenced group), neonatal discharge and 12 months postpartum\*
- 7. Depression following result disclosure (or 4 weeks post enrollment for the unsequenced group), neonatal discharge and 12 months postpartum\*
- 8. Quality of life for the patient and family at 12 months postpartum\*
- 9. Incremental cost per Quality Adjusted Life Year (QALY)
- \* Only available on participants enrolled prospectively and followed through 12 months postpartum

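### QALYs are defined only through conditions found by sequencing, so the increment between sequenced and unsequenced pregnancies is either undefined or depends on how often disease is detected in each group

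*Combined protocol and SAP*

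**What the plan says.** All references are to Version 1.8 of the protocol unless stated otherwise.

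Section 5.3.1 makes QALYs the effect measure. Maternal and neonatal QALYs come from published utility weights, on a scale from 0 for death to 1 for perfect health, taken "from various health states to components of the conditions found by sequencing". No other source of QALYs appears anywhere in the document. The same section then states: "Cost-effectiveness of prenatal sequencing will be evaluated as the incremental cost per QALY", with a threshold of $100,000 per QALY.

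Section 4.10.2 lists this ratio as secondary outcome 9, among the outcomes for both groups. It lacks the asterisk that marks outcomes available only for prospectively enrolled participants.

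On the comparator, section 3.1 says that the remaining "350 pregnancies will not have any prenatal genomic sequencing". Section 4.2.2 allows postpartum genomic sequencing at the clinical team's discretion, and Table 2 in section 4.6 has those results collected. Section 4.6 adds: "Women who are enrolled retrospectively will be followed from screening through delivery discharge".

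Section 5.3.1 also describes sensitivity analyses. These vary the baseline risk of sequencing findings and the change in neonatal outcomes, and use Monte Carlo sampling within a model. The model's structure, its parameter values and the QALY time horizon are not given. The QALY rule reads the same in Version 1.0.

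**The concern.** An incremental cost per QALY needs a QALY value for every pregnancy in both groups, obtained in the same way. The stated rule starts from a sequencing finding. It therefore has nothing to apply to an unsequenced pregnancy without postnatal sequencing, or to a sequenced pregnancy with a negative result. It also does not say whether a variant of uncertain significance counts as a condition.

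The two groups differ by design in how often a condition can be found. One is sequenced systematically; the other is sequenced after birth only if a clinician orders it. If the utility attached to an infant depends on whether a condition was found, two infants with the same disorder and the same course can receive different QALYs. The difference between groups would then partly measure detection rather than health.

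Section 2.3 presents this as the first cost-effectiveness analysis of its kind. Without a rule fixed in advance, whoever runs the analysis must choose the comparator's QALYs after the data are in, and that choice could settle the conclusion.

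**Working it through.** The plan states no QALY value, utility, time horizon or cost-effectiveness ratio, so there is no figure to reproduce. The check has two parts.

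**Coverage of the rule.** Section 5.1 bases its yield on 22 diagnoses in 234 trios: 22/234 = 9.4%. Applied to the 750 sequenced pregnancies, that is 0.094 × 750 = 70.5 with a diagnosis and 750 − 70.5 = 679.5 without. The rule as worded thus covers about 70 sequenced pregnancies, plus those of the 350 unsequenced whose infants are sequenced clinically and found to have a condition. That last number is not stated.

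**Size of a detection artefact.** Suppose true health is identical in both groups, so the correct QALY difference is zero. Take a one-year horizon and define:

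- y: share with a causal condition, 9.4% (section 5.1), all found in the sequenced group;
- u: utility of such a condition, assumed 0.5 to 0.9;
- q: share of these conditions found by postnatal clinical sequencing in the unsequenced group, assumed 0 to 1;
- everyone without a found condition is valued at 1 (assumed).

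Mean QALY, sequenced: 1 − y(1 − u).

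Mean QALY, unsequenced: 1 − yq(1 − u).

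Difference (sequenced minus unsequenced): −y(1 − q)(1 − u).

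| u | q = 0 | q = 0.5 | q = 1 |
|---|---|---|---|
| 0.5 | −0.047 | −0.0235 | 0 |
| 0.7 | −0.0282 | −0.0141 | 0 |
| 0.9 | −0.0094 | −0.0047 | 0 |

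For example, with u = 0.5 and q = 0: 0.094 × 1 × 0.5 = 0.047.

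If unfound conditions are valued at some v between u and 1, the difference becomes −y(1 − q)(v − u). It shrinks as v approaches u and is zero at v = u. Giving both groups the same condition prevalence and the same utilities amounts to v = u, so the artefact vanishes. If unfound conditions receive no value at all, the unsequenced mean and the ratio are undefined.

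**The case against.** The best defence is that section 5.3.1 describes a decision model rather than a tally of findings patient by patient. Parameters are sampled within a model, acceptability curves are drawn, and both the baseline risk of findings and the change in neonatal outcomes are varied. On that reading, sequencing only shows which conditions need utilities, both strategies share one prevalence, and sequencing acts through changed outcomes. The artefact would then be zero. This reading is possible, and it limits what can be claimed. It does not close the gap: the model is not described, no comparator value is given, and varying the parameters of an unspecified model does not define its base case.

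Second, a reader might infer that the unsequenced group has no effect measure at all. The documents do not support that. The rule speaks of sequencing, not prenatal sequencing, and postnatal results are collected. What holds is that no method is specified for those without such a result.

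Third, a reader might infer that sequencing is bound to lose QALYs by finding disease. That requires unfound conditions to be valued nearer to full health than found ones. The plan does not say so, and it would be an odd choice in a cohort where every fetus was enrolled for an abnormal finding. The plan does not rule it out either.

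Fourth, the missing asterisk on outcome 9 is not in itself an error. QALYs modelled from published weights need no individual follow-up after discharge.

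**Conclusion.** The point holds as a fault in how the effect measure is defined. The only QALY rule depends on sequencing findings, while the outcome compares a group sequenced by design with one sequenced only after birth and at clinical discretion. As written, the increment is undefined or depends on differential detection.

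The possible penalty to sequencing is 0 to 0.047 QALY per pregnancy-year. The yield is the plan's; the utilities, the postnatal detection share, the one-year horizon, equal true health and full-health valuation of unfound conditions are assumptions. The lower end is a genuine possibility, reached with full postnatal detection or a shared prevalence. A certain bias against sequencing cannot be claimed. Nor can a dollar amount over several years, because the plan gives no horizon over which to accumulate it. If a negative artefact did arise alongside a positive incremental cost, sequencing would appear both costlier and worse despite equal health.

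Neither primary outcome is affected. The correction should be made before the cost-effectiveness analysis is run.

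**What to change.** Replace the QALY sentence in section 5.3.1 with a rule that:

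- assigns utilities in both groups by the same algorithm, regardless of any sequencing result;
- uses states recorded alike in both groups: survival, anomaly type, and the neonatal and maternal outcomes collected through discharge;
- uses the same weights and one fixed time horizon common to both groups;
- where conditions are modelled beyond the observed period, gives both groups the same underlying prevalence, so that sequencing changes QALYs only through changed outcomes;
- restricts any QALY analysis that uses observed 12-month data to prospectively enrolled participants, and says so at outcome 9.

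Discharge should not be the horizon, although it is where follow-up of the retrospective controls ends. It would depend on length of stay, so a sicker infant who stays longer would accrue more life-years than one sent home early. It would also nearly remove the effect measure: with an assumed 30-day stay, even an averted death is worth at most 30/365, about 0.08 QALY.

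The cost is a change of analysis wording and a different utility look-up. No new data are needed for the states through discharge. The drawback is that utilities by phenotype and morbidity are coarser than condition-specific ones.

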#### 5 Statistical Considerations

# 5.1 Power and sample size

The first primary outcome for this study is the frequency of pathogenic, likely pathogenic, or VUS genomic variants identified by sequencing among participants with a normal karyotype and CMA. The sample size is based on the incremental yield reported in a prospective study of WES performed at Columbia University in a similar population. Among 234 parent-fetus trios without CMA abnormalities, a genetic diagnosis was reported in 22 (9.4%). The precision of the estimate for a range of sample sizes and estimates is shown in Table 4. An estimate of 9.4% and sample size of 750 in the prenatal sequenced group will have a precision of 2.3% (confidence interval half-width) with a 93% probability.

Estimate	Sample size	Cl ½-width
9.0%	700	2.4%
	750	2.3%
	800	2.2%
9.4%	700	2.4%
	750	2.3%
	800	2.3%
9.8%	700	2.5%
	750	2.4%
	800	2.3%

The second primary outcome is maternal and neonatal hospital charges. The utilization of health care and cost only will include women that deliver at one of the study centers. Given that some of the recruiting centers include referrals in which the women will not deliver at the study center, power estimates assume cost will be available on 500 of the 750 in the prenatal sequencing group. Similarly, of the 350 unsequenced prenatal controls, 15% are assumed to have a pathogenic or likely pathogenic causal pre-/postnatal CMA prior to neonatal discharge or deliver elsewhere resulting in approximately 300 unsequenced prenatal controls available for analysis. The total charges for deliveries at Columbia University that required a NICU admission in 2016 and 2017 (partial year) were used to provide cost estimates. The charges follow a lognormal distribution approximately with a mean total charge of \$277,902 and standard deviation of \$389,484. Assuming 500 participants in the prenatal WGS group, and 300 unsequenced prenatal control participants, the study will have 80% power to detect a mean ratio of 0.80 (20% reduction) with an alpha=0.05 two-sided.

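### The $100,000-per-QALY rule ignores the sign of the QALY difference, so it gives the wrong verdict if sequencing is associated with fewer QALYs

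*Combined protocol and SAP*

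**What the plan says.** Incremental cost per QALY is secondary outcome 9 in section 4.10.2 of the current protocol (Version 1.8). Section 5.3.1 gives the only decision criterion for it: "Cost-effectiveness of prenatal sequencing will be evaluated as the incremental cost per QALY with a threshold of less than" a dollar amount, completed by "100,000 per QALY as cost effective". Maternal and neonatal QALYs are to be derived from published utility weights. The section does not say what happens if the QALY difference is zero or negative.

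The same section promises means with 95% confidence intervals for costs and outcomes. It also plans one-way sensitivity analyses and a Monte Carlo simulation that will "report 95% confidence ellipses and acceptability curves". It does not say how the acceptability curves are to be constructed.

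**The concern.** A ratio of two differences loses the information in their signs. A negative ratio can mean cheaper and better, or dearer and worse. A positive ratio can mean paying for a gain, or saving money at a loss. Comparing the ratio with a single upper limit is sound only when its denominator is positive.

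Two things are at stake. The first is the base-case statement of whether sequencing is cost effective. The second is the acceptability curve: if it is built by counting the Monte Carlo draws whose ratio is below the threshold, every draw with a negative QALY difference is counted on the wrong side.

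**Working it through.** The plan attaches no figure to this rule, so there is none to reproduce. The check compares the written rule with a rule that respects the signs.

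**Inputs**
- Threshold L = $100,000 per QALY (section 5.3.1).
- dC = cost difference and dQ = QALY difference, each sequenced minus unsequenced. The documents give no value of dQ, so all values below are assumptions.
- Two cost figures serve for scale only. Section 2.2.3 prices sequencing at $15,000 or more per trio. Section 5.1 gives a mean total charge of $277,902 and powers the charge comparison for a 20% reduction, which is 0.20 x 277,902 = $55,580. Charges stand in for costs here. The other cost differences are assumed.

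**Algebra**
- Written rule: accept if dC/dQ < L.
- Net monetary benefit: NMB = L x dQ - dC; accept if NMB > 0.
- If dQ > 0, multiplying dC/dQ < L by dQ gives dC < L x dQ, which is NMB > 0. The rules are identical.
- If dQ < 0, the same step flips the inequality to dC > L x dQ, which is NMB < 0. The written rule accepts exactly what net benefit rejects.
- If dQ = 0, the ratio is undefined, while NMB = -dC.

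**Numbers**

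| dC ($) | dQ | dC/dQ ($) | Written rule | NMB ($) | Net benefit |
|---|---|---|---|---|---|
| +15,000 | +0.30 | 50,000 | accept | +15,000 | accept |
| +15,000 | +0.05 | 300,000 | reject | -10,000 | reject |
| -55,580 | +0.30 | -185,267 | accept | +85,580 | accept |
| +20,000 | -0.1 | -200,000 | accept | -30,000 | reject |
| +15,000 | -0.05 | -300,000 | accept | -20,000 | reject |
| -20,000 | -0.1 | 200,000 | reject | +10,000 | accept |
| -5,000 | -0.1 | 50,000 | accept | -5,000 | reject |
| -55,580 | -1.0 | 55,580 | accept | -44,420 | reject |

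The first three rows agree and the last five do not. With a saving of $55,580, the break-even loss is 55,580/100,000 = 0.556 QALY. Net benefit favours sequencing below that loss and rejects it above; the written rule does the opposite.

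A grid with dC from -$60,000 to +$60,000 and dQ from -1 to +1 confirms the algebra. The two rules agree at 100% of points in both quadrants with dQ > 0, and at 0% in both quadrants with dQ < 0.

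**The case against.** The strongest reply is that no competent health economist would apply the sentence mechanically. The usual meaning is cost per QALY gained, and dominance would be recognised without being written down. The means, confidence intervals and ellipses would also show the direction of both differences. This stands in part: an unnoticed reversal is unlikely, and nothing suggests an intention to call a dominated strategy cost effective. But these outputs describe the result and do not define the verdict, and the acceptability curves avoid the fault only if they are built from net benefit, which the plan does not say.

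Three stronger readings are tempting and are not supported.
- **That a principal result is at risk.** The outcome is ninth in the list of secondary outcomes. The primary cost outcome is hospital charges, which this rule does not touch.
- **That the hoped-for cost reduction makes a QALY loss likely.** A hypothesis about cost says nothing about the sign of the QALY difference. Section 1.1 hypothesises lower cost together with better care and quality of life. Section 2.2.3 anticipates either a saving, or a higher cost justified by better outcomes. The written rule works in those quadrants.
- **That the companion cost-benefit ratio in section 5.3.1 has the same fault.** It divides by the cost of usual care, not by a difference that can change sign.

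**Conclusion.** The point holds as a safeguard on a secondary conclusion. As written, the rule is right for every positive QALY difference and wrong for every negative one, in both the costlier and the cheaper case (points exactly at the threshold aside). That follows from algebra and does not depend on the assumed values, which show only how the error looks.

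The documents do not predict a QALY loss, but they do not rule one out either. Section 5.3.1 puts no restriction on sign, counts maternal as well as neonatal QALYs, and varies the change in neonatal outcomes in sensitivity analysis. A negative difference could therefore arise in the base case or in individual Monte Carlo draws. How often it would arise cannot be judged from the documents, so no probability of a wrong conclusion can be given.

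**What to change.** In section 5.3.1, state the decision rule as incremental net monetary benefit: sequencing is cost effective at the chosen threshold if $100,000 x (QALY difference) - (cost difference) > 0. Report it with a 95% interval taken from the Monte Carlo simulation already planned, and say that the acceptability curves are built from net benefit. The simulation is the natural source of the interval, because the plan takes utilities from publications and describes no participant-level QALY.

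Keep the incremental cost per QALY as a reported quantity, with its quadrant. Write dominant or dominated in words where that applies. When both differences are negative, neither word fits, and net benefit should decide.

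The cost is a few sentences and a small amount of extra analysis, with no new data. No sample size or primary analysis changes.
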